### **16.6.2 Serious Adverse Event (SAE)**

Information about all serious adverse events will be collected and recorded. A serious adverse event is an undesirable sign, symptom or medical condition which:

- Is fatal or life-threatening
- Results in persistent or significant disability/incapacity
- Is medically significant, i.e., defined as an event that jeopardizes the patient or may require medical or surgical intervention to prevent one of the outcomes listed above
- Causes congenital anomaly or birth defect
- Requires inpatient hospitalization or prolongation of existing hospitalization, unless hospitalization is for:

- Routine treatment or monitoring of the studied indication, not associated with any deterioration in condition (procedures such as central line placements, paracentesis, pain control)
- Elective or pre-planned treatment for a pre-existing condition that is unrelated to the indication under study and has not worsened since the start of study drug
- Treatment on an emergency outpatient basis for an event not fulfilling any of the definitions of a SAE given above and not resulting in hospital admission
- Social reasons and respite care in the absence of any deterioration in the patient's general condition

Collection of serious adverse events will begin after the first dose and end 90 days after the last dose of study treatment or until a new cancer treatment is initiated, whichever happens the soonest.

Any death from any cause while a patient is receiving treatment on this protocol or up to 30 days after the last dose of protocol treatment, or any death which occurs more than 30 days after protocol treatment has ended but which is felt to be treatment related, must be reported.

Toxicities which fall within the definitions listed above must be reported as an SAE regardless if they are felt to be treatment related or not. Toxicities unrelated to treatment that do NOT fall within the definitions above, must simply be documented as AEs in the patient research chart.

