### 5.1 Inclusion Criteria

**Yes/No (Response of "no" = patient ineligible)**

**5.1.1** \_\_\_\_\_ Histologically confirmed, metastatic or unresectable neuroendocrine carcinoma of non-pulmonary origin, high grade as indicated by Ki-67 >20% and/or > 20 mitoses/10 hpf. Patients must have existing Ki-67 results from archival tissue or available tissue for Ki-67 testing. If no archival tissue is available the subject must agree to a fresh biopsy for testing to qualify for the study.

**5.1.2** \_\_\_\_\_ Patients must have progressed during or after first-line treatment for metastatic or unresectable disease with either a platinum-based regimen (e.g. carboplatin + VP16, cisplatin + VP-16, FOLFOX) OR temozolomide-based regimen. Patients must have failed at least one line of therapy but no maximum number of therapies is exclusionary (i.e. second-line therapy and beyond).

**5.1.3** \_\_\_\_\_ Have measurable disease based on irRECIST.

**5.1.4** \_\_\_\_\_ Be  $\geq$  18 years of age on day of signing informed consent.

**5.1.5** \_\_\_\_\_ Have a performance status of 0 or 1 on the ECOG Performance Scale.

**5.1.6** \_\_\_\_\_ Demonstrate adequate organ function as defined in Table 2, all screening labs should be performed within 14 days of treatment initiation.

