## 10 STUDY PROCEDURES

### 10.1 Screening Evaluations

- Informed Consent
- Physical examination with vital signs and ECOG Performance Status
- Review of medical history/baseline symptoms
- Review baseline concomitant medications
- Laboratory assessments:
  - CBC with differential
  - CMP to include sodium, potassium, chloride, carbon dioxide or bicarbonate, blood urea nitrogen (BUN), creatinine, glucose, total protein, albumin, calcium, AST, ALT, alkaline phosphatase, total bilirubin
  - Coagulation to include PT/INR and aPTT
  - Thyroid function tests to include TSH, total T3, and free T4
  - Serum or urine pregnancy test (for women of childbearing potential) within 72 hours of starting study treatment
  - Urinalysis
- 12-lead ECG if clinically indicated
- CT scans and disease assessments for baseline irRECIST
- MRI only for subjects with previously treated brain metastases
- Archival tissue or fresh tissue biopsy (if archival tissue is not available) for Ki-67 testing (see footnote #8 in calendar)
- Archival tissue or fresh biopsy for central PD-L1 analysis if patients consent to optional testing.

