##### **15.4.1.1 Fresh tissue biopsy (if archival tissue is not available for Ki-67 testing)**

- 1-2 cores with an 18 gauge needle.
- .

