### **16.6.1 Adverse Events (AEs)**

An adverse event is the appearance or worsening of any undesirable sign, symptom, or medical condition occurring after starting the study drug even if the event is not considered to be related to study drug. For the purposes of this study, the terms toxicity and adverse event are used interchangeably. Medical conditions/diseases present before starting study drug are only considered adverse events if they worsen after starting study drug. Abnormal laboratory values or test results constitute adverse events only if they induce clinical signs or symptoms, are considered clinically significant, or require therapy.

The collection of adverse events will begin after the first dose of study treatment and end 30 days post the last dose of study treatment.

Information about all adverse events, whether volunteered by the subject, discovered by investigator questioning, or detected through physical examination, laboratory test or other means, will be collected and recorded and followed as appropriate.

The occurrence of adverse events should be sought by non-directive questioning of the patient at each visit or phone contact during the study. Adverse events also may be detected when they are volunteered by the patient during or between visits or through physical examination, laboratory test, or other assessments. As far as possible, each adverse event should be evaluated to determine:

1. The severity grade based on CTCAE v.4 (grade 1-5)
2. Its relationship to the study drug(s) (definite, probable, possible, unlikely, not related)
3. Its duration (start and end dates or if continuing at final exam)
4. Action taken (no action taken; study drug dosage adjusted/temporarily interrupted; study drug permanently discontinued due to this adverse event; concomitant medication taken; non-drug therapy given; hospitalization/prolonged hospitalization)
5. Whether it constitutes an SAE

All adverse events will be treated appropriately. Such treatment may include changes in study drug treatment as listed in the dose modification section of this protocol (see section 8 for guidance). Once an adverse event is detected, it should be followed until its resolution, and assessment should be made at each visit (or more frequently, if necessary) of any changes in severity, the suspected relationship to the study drug, the interventions required to treat it, and the outcome.

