**16.10 Reporting of Pregnancy and Lactation to HCI Sponsor, IRB, DSMC and Merck**

Although pregnancy and lactation are not considered adverse events, it is the responsibility of investigators or their designees to report any pregnancy or lactation in a subject (spontaneously reported to them) that occurs during the trial.

Pregnancies and lactations that occur after the consent form is signed but before treatment allocation/randomization must be reported by the investigator if they cause the subject to be excluded from the trial, or are the result of a protocol-specified intervention, including but

not limited to washout or discontinuation of usual therapy, diet, placebo treatment or a procedure.

Pregnancies and lactations that occur from the time of treatment allocation/randomization through 120 days following cessation of Sponsor's product, or 30 days following cessation of treatment if the subject initiates new anticancer therapy, whichever is earlier, must be reported by the investigator. All reported pregnancies must be followed to the completion/termination of the pregnancy. Pregnancy outcomes of spontaneous abortion, missed abortion, benign hydatidiform mole, blighted ovum, fetal death, intrauterine death, miscarriage and stillbirth must be reported as serious events (Important Medical Events). If the pregnancy continues to term, the outcome (health of infant) must also be reported.

Such events must be reported within 24 hours to the Sponsor, DSMC and IRB and within 2 working days to Merck Global Safety. (Attn: Worldwide Product Safety; [contact] or [AER\\[contact]](mailto:[contact]))

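### Serious complications of the required screening biopsy that occur before the first dose, and do not worsen after it, fall outside SAE collection

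*Combined protocol and SAP*

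**What the plan says.** **When collection starts.** Section 16.6.2: "Collection of serious adverse events will begin after the first dose and end 90 days after the last dose of study treatment", or when a new cancer treatment starts, if sooner. Section 16.6.1: "The collection of adverse events will begin after the first dose of study treatment"; it closes 30 days after the last dose.

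**What counts as an adverse event.** Section 16.6.1 covers an undesirable sign, symptom or "condition occurring after starting the study drug even if the event is not considered to be related to study drug". It adds: "Medical conditions/diseases present before starting study drug are only considered adverse events if they worsen after starting study drug". Causality is graded against study drug only.

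**What may happen before the first dose.** Section 5.1.1 requires an existing Ki-67 result or tissue for the test: "If no archival tissue is available the subject must agree to a fresh biopsy for testing to qualify for the study". Section 10.1 lists this among the screening evaluations: "Archival tissue or fresh tissue biopsy (if archival tissue is not available) for Ki-67 testing". Section 15.4.1.1 specifies the procedure: "1-2 cores with an 18 gauge needle". Section 13 allows study screening procedures only after consent.

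**What is recorded at screening.** The calendar in Section 9 has a medical history and baseline AE entry in the Screening column. The row for review of adverse events and events of clinical interest begins at cycle 1.

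**The concern.** A biopsy done only to qualify for the trial is an invasive research procedure in a consented participant. Participants and the DSMC would expect serious harm from it to be reported as a trial event. As written, the trigger for collection is the first dose of drug, not consent or the first study procedure. A bleed that needs admission a few days after the biopsy would meet the hospitalization criterion for seriousness but fall before the window opens. If the patient is then too unwell to be treated, the window never opens at all.

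What is at stake is oversight of harm caused by the trial's own screening. This is a stated rule with a definite start date, not a detail left unspecified, so sites that follow it correctly will leave such events out.

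**Working it through.** The plan states no figure on this point to reproduce. The check is whether any provision captures a serious biopsy complication that begins between consent and the first dose.

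**Step 1: the main rules.**
- AE definition (16.6.1): no, because the event precedes study drug. If it later worsens on drug, yes.
- AE window (16.6.1) and SAE window (16.6.2): no, because both open after the first dose. The list of seriousness criteria in 16.6.2 has no time limit of its own; the limit comes from the collection window and from the AE definition.

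**Step 2: the other routes.**

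| Provision | Captures the event? |
|---|---|
| Death reporting (16.6.2) | No. It covers deaths on treatment, within 30 days after the last dose, or later if felt to be treatment related |
| Events of clinical interest (16.8) | No. The period runs from the first dose, and the two listed events are overdose and a pattern of liver tests |
| FDA notification (16.7) | No. The event must be at least possibly related to the investigational drug |
| DSMC review (16.5) | No rule found. It works from SAEs as defined, and from toxicities on treatment and within a 30-day follow-up |
| Manufacturer notification (16.7) | No. It applies to SAEs and events of clinical interest |
| Deviation reporting (16.12) | No. A complication of a biopsy done as specified is not a departure from the protocol |
| Baseline AE entry (Section 9) | Recorded at screening, but not as an SAE and with no onward report |
| IRB notification (16.7) | Possibly. It refers to IRB requirements that are not in the document |

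**Step 3: length of the uncovered period.** Inputs: screening procedures are to be completed within 4 weeks of enrollment (Section 9, footnote 1), and treatment should begin within 5 days of registration (Section 13). Assumption: enrollment and registration fall on the same date. Then

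4 × 7 + 5 = 33 days.

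This is a maximum, reached only if the biopsy is done on the first permitted day.

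**Step 4: how many patients.** The document gives neither the share needing a fresh biopsy nor a complication rate. It gives up to 40 enrolled (4.2, Section 12) but no number consented. For illustration only, assume 40 to 50 consented, 10% to 30% biopsied, and a serious complication rate of 1% to 3%:

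- biopsied: 0.10 × 40 = 4 to 0.30 × 50 = 15;
- expected serious events in the whole trial: 4 × 0.01 = 0.04 to 15 × 0.03 = 0.45.

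Every rate in this step is assumed. The conclusion does not depend on them.

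**The case against.** The strongest reply is that a reader might infer such harm is never reported and that nothing reaches the IRB. The document does not support that. Section 16.7 has a separate IRB route, with local IRB rules for external sites, and the content of those requirements cannot be seen here. The NCI-approved plan that sets the DSMC's role is likewise outside the document. Screening records baseline events. Concomitant medications are recorded for 28 days before the first dose (7.7.1), so treatment of a complication may leave a trace. A complication that arises or worsens after the first dose is captured, and if serious it is an SAE whatever its cause. All of this stands. It limits the gap, but none of it is a rule that collects a pre-dose biopsy injury as an SAE or sends it to the DSMC or the manufacturer.

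A reader might also infer that the safety objective is compromised. It is not: objective 1.2.4 concerns safety and tolerability of pembrolizumab, and harm before any drug is not part of that.

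Nor are losses between consent and first dose simply hidden. Under Section 13 the Research Compliance Office confirms slots, verifies eligibility and is told of cancelled registrations, although no reason for the loss need be recorded.

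Finally, Section 16.10 requires reporting of some pregnancies between consent and allocation, including those that "are the result of a protocol-specified intervention". It is tempting to call this a contradiction. It is not, since the section says pregnancy is not an adverse event, and its references to randomization and placebo do not fit this single-arm trial. It shows only that reporting from consent has a precedent within the protocol.

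The objection that few patients are affected is fair. Every patient has histologically confirmed, previously treated disease, and an existing Ki-67 result or archival tissue is enough.

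**Conclusion.** The gap is real and narrow. A serious event caused by the required screening biopsy that occurs before the first dose and does not worsen afterwards lies outside the AE definition and the SAE collection window, and no other rule in the document requires it to be collected as an SAE or sent to the DSMC or the manufacturer. It matters most for a patient who is harmed and never dosed, because no later event can bring that patient into the window.

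The exposure lasts at most about 33 days per patient, on the assumption that enrollment and registration coincide. The number affected is not stated and is probably small; under the illustrative rates above, fewer than one serious event would be expected. Sample size, error rates, the response analysis and the pembrolizumab safety tabulation are unaffected. The case for change is oversight of participants, and the change is cheap.

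**What to change.** 1. **Section 16.6.2:** from signed consent to first dose, collect SAEs, including deaths, caused by a protocol-required procedure such as the fresh biopsy in 5.1.1, and report them under 16.7. Leave the existing window after the first dose unchanged.
2. **Section 16.6.1:** amend the AE definition and start of collection to allow this exception. Otherwise the new sentence in 16.6.2 would contradict them.
3. **Causality (16.6.1):** add a category for relationship to a study procedure, since the present scale refers to study drug only.
4. **Section 9:** add a matching check for procedure-related serious events to the Screening column.
5. **Reporting:** list these events separately from treatment-emergent events, so that the pembrolizumab safety table does not change.

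The cost is amendment wording and a few extra report forms. No new visit, test or patient is needed.

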### **7.7.2 Prohibited Concomitant Medications**

Subjects are prohibited from receiving the following therapies during the Screening and Treatment Phase (including retreatment for post-complete response relapse) of this trial:

- Antineoplastic systemic chemotherapy or biological therapy. Hormonal therapies or other long-term adjuvant therapies may be approved after discussion with the principal investigator.
- Immunotherapy not specified in this protocol
- Chemotherapy not specified in this protocol
- Investigational agents other than pembrolizumab
- Radiation therapy
  - Note: Radiation therapy to a symptomatic solitary lesion or to the brain may be allowed at the investigator's discretion.
- Live vaccines within 30 days prior to the first dose of trial treatment and while participating in the trial. Examples of live vaccines include, but are not limited to, the following: measles, mumps, rubella, varicella/zoster, yellow fever, rabies, BCG, and typhoid vaccine.
- Systemic glucocorticoids for any purpose other than to modulate symptoms from an event of clinical interest of suspected immunologic etiology. The use of physiologic doses of corticosteroids may be approved after consultation with the study sponsor (principal investigator).

Subjects who, in the assessment by the investigator, require the use of any of the aforementioned treatments for clinical management should be removed from the trial. Subjects may receive other medications that the investigator deems to be medically necessary.

The Exclusion Criteria describes other medications which are prohibited in this trial.

There are no prohibited therapies during the Post-Treatment Follow-up Phase.

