## **7.8 Duration of Therapy**

A subject must be discontinued from the trial for any of the following reasons:

- The subject or legal representative (such as a parent or legal guardian) withdraws consent.
- Radiographic disease progression by irRECIST (progression must be confirmed with follow up scan no less than 4 weeks and no more than 8 weeks after the first scan shows disease progression)
- Unacceptable adverse experiences as described in Section 8.1
- Intercurrent illness that prevents further administration of treatment
- Investigator's decision to withdraw the subject
- The subject has a confirmed positive serum pregnancy test
- Noncompliance with trial treatment or procedure requirements
- The subject is lost to follow-up
- Completed 24 months of uninterrupted treatment with pembrolizumab or 35 administrations of study medication, whichever is later.

*Note: 24 months of study medication is calculated from the date of first dose.*

- Administrative reasons

The End of Treatment and Follow-up visit procedures are listed in Section 9 (Protocol Calendar). After the end of treatment, each subject will be followed for 30 days for adverse event monitoring (serious adverse events will be collected for 90 days after the end of treatment or until a new cancer treatment is started, if sooner). Subjects who discontinue for reasons other than progressive disease will have post-treatment follow-up for disease status until disease progression, initiating a non-study cancer treatment, withdrawing consent or becoming lost to follow-up. After documented disease progression each subject will be followed for overall survival, withdrawal of consent, or the end of the study, whichever occurs first.

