## **16.8 Events of Clinical Interest (ECI)**

Selected non-serious and serious adverse events thought to be related to Pembrolizumab are also known as Events of Clinical Interest (ECI) and must be recorded as such on the Adverse Event case report forms/worksheets and reported within 24 hours to the HCI Principal Investigator and research compliance office and within 2 working days of first knowledge or notification of event to Merck Global Safety. (Attn: Worldwide Product Safety; [contact] or [AER\\[contact]](mailto:[contact]))

Events of clinical interest for this trial include:

1. An overdose of Merck product, as defined in Section 16.7 - Definition of an Overdose for This Protocol and Reporting of Overdose to the Sponsor, that is not associated with clinical symptoms or abnormal laboratory results.
2. An elevated AST or ALT lab value that is greater than or equal to 3X the upper limit of normal and an elevated total bilirubin lab value that is greater than or equal to 2X the upper limit of normal and, at the same time, an alkaline phosphatase lab value that is less than 2X the upper limit of normal, as determined by way of protocol-specified laboratory testing or unscheduled laboratory testing.\*

**\*Note:** these criteria are based upon available regulatory guidance documents. The purpose of the criteria is to specify a threshold of abnormal hepatic tests that may require an additional evaluation for an underlying etiology.

ECIs that occur in any subject from the date of first dose through 90 days following cessation of treatment, or the initiation of a new anticancer therapy, whichever is earlier, whether or not related to the Merck's product, must be reported within 24 hours to the HCI and to Merck Global Safety within 2 working days of first knowledge or notification of event

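### SAE and ECI collection stops when new cancer treatment starts, with no 30-day minimum, so after an early switch serious events have a shorter window than ordinary AEs

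*Combined protocol and SAP*

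**What the plan says.** All references are to the combined protocol and SAP.

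- **AEs.** Under Section 16.6.1, collection is to "end 30 days post the last dose of study treatment". Section 7.8 agrees: after treatment ends, "each subject will be followed for 30 days for adverse event monitoring". Neither mentions new therapy.
- **SAEs.** Under Section 16.6.2, collection is to "end 90 days after the last dose of study treatment or until a new cancer treatment is initiated, whichever happens the soonest". Section 7.8 gives the same rule: "serious adverse events will be collected for 90 days after the end of treatment or until a new cancer treatment is started, if sooner".
- **ECIs.** Section 16.8 runs from first dose "through 90 days following cessation of treatment, or the initiation of a new anticancer therapy, whichever is earlier".
- **Deaths.** Section 16.6.2 requires reporting of a death from any cause on treatment "or up to 30 days after the last dose of protocol treatment", with no cut-off at new therapy. Later deaths are named if they are thought to be treatment related.
- **Pregnancy and lactation.** Section 16.10 sets 120 days, "or 30 days following cessation of treatment if the subject initiates new anticancer therapy".
- **DSMC.** Section 16.5 has the committee review toxicities on treatment and for 30 days afterwards, with no cut-off at new therapy.
- **Later treatment.** Section 7.7.2 states: "There are no prohibited therapies during the Post-Treatment Follow-up Phase".

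**The concern.** A serious-event window is normally at least as long as the window for ordinary events. Here 90 days against 30 shows that intent, and Section 7.7.1 assumes it too: concomitant medication is recorded to day 30 and, after that, only for SAEs and ECIs. But the SAE and ECI rules can be cut short by new treatment and the AE rule cannot, so an early switch reverses the order.

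Take a patient who starts chemotherapy on day 15 and is admitted with colitis on day 20. The event is inside the AE window and outside the SAE window. SAE status is what triggers the duties in Section 16.7: the MedWatch form within 1 working day, the summary to the DSMC, FDA reports at 7 or 15 calendar days where the event is also unexpected and related, and notice to the manufacturer within 2 working days. The site has one section that tells it to record the event and ask whether it is serious, and another that says SAE collection has closed.

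What is at stake is consistent, timely reporting of non-fatal serious events in patients who switch quickly. Safety and tolerability is secondary objective 1.2.4.

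**Working it through.** There is no planned figure to reproduce. The check compares the windows.

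**Inputs**
- Let t be the number of days from the last dose to new cancer treatment.
- AE window: A = 30 (Sections 16.6.1 and 7.8).
- SAE and ECI window: S(t) = min(90, t) (Sections 16.6.2, 7.8 and 16.8). With no new therapy, S = 90.
- The sections count from the last dose, the end of treatment or cessation of treatment. I take these as the same day.

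**Comparison.** The last column is the window with a 30-day minimum, max(30, min(90, t)).

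| t (days) | AE window | SAE/ECI window | SAE/ECI minus AE | With 30-day minimum |
|---|---|---|---|---|
| 14 | 30 | 14 | -16 | 30 |
| 21 | 30 | 21 | -9 | 30 |
| 30 | 30 | 30 | 0 | 30 |
| 60 | 30 | 60 | +30 | 60 |
| no new therapy | 30 | 90 | +60 | 90 |

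The order is reversed for every t below 30 and for no t of 30 or more. With the minimum it is never reversed.

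**Can t be below 30?** Yes. Section 7.7.2 allows any therapy in follow-up, and no interval after the last dose is required before new treatment. It also says that subjects who need a prohibited treatment, such as chemotherapy, should be removed from the trial. Section 7.8 lists reasons for stopping other than confirmed progression, including unacceptable toxicity and investigator decision.

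**How often?** The documents give no distribution of time to next therapy. They allow only two bounding cases for patients who stop for progression. Doses are 21 days apart and scans fall in the 7 days before the next dose (Section 9, footnote 10), so a scan falls 14 to 21 days after the preceding dose, ignoring the 3-day visit window.
- *Dosing continues up to the scan that ends treatment.* Then t is below 30 if new therapy starts less than 9 days (30 - 21) to 16 days (30 - 14) after that scan.
- *Dosing is held from first progression until confirmation.* Section 7.8 places confirmation 4 to 8 weeks (28 to 56 days) after the first scan. That is day 42 (14 + 28) to day 77 (21 + 56) after the last dose. New therapy after confirmation then falls beyond day 30 and nothing is reversed.

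**Which events are affected?** Deaths to day 30 are reported regardless, so the gap concerns non-fatal SAEs and ECIs. Section 16.8 lists two ECIs. An overdose cannot newly arise after the last dose, so in practice the ECI gap is the liver-test pattern. Colitis and pneumonitis are not listed ECIs; they matter here when they meet an SAE criterion such as hospitalisation.

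**The case against.** The strongest reply is that the information is still collected. Section 16.6.1 captures all adverse events to day 30, with grade, relationship, action taken (including hospitalisation) and a judgement on seriousness, and follows them to resolution. Section 16.6.2 adds that toxicities meeting the SAE definitions are to be reported as SAEs whether or not they are thought related. The planned safety analysis in Section 12 tabulates adverse events, the DSMC reviews toxicities for 30 days after treatment, and the FDA criteria in Section 16.7 do not refer to the SAE collection window. All of this stands. The event need not disappear from the AE tabulation, and a careful site may well report it as an SAE. What remains is that the stated SAE window has closed and no sentence says which provision prevails.

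A second reply is that stopping at new therapy is deliberate, since later events are hard to attribute. The rule is indeed the same in Sections 7.8, 16.6.2 and 16.8. But attribution is no easier for ordinary AEs, which are collected to day 30 regardless, and the provisions for deaths, pregnancy and DSMC review each keep 30 days. The pregnancy rule serves another purpose, so it shows that a 30-day minimum is workable here; it does not contradict the SAE rule.

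A reader might infer that the death sentence contradicts the SAE rule for an unrelated death on, say, day 60 without new therapy. The text does not support that. The sentence lists deaths that must be reported and does not say that no others are. Read as an addition to the SAE rule, it leaves such a death reportable as a fatal SAE. At most the wording could say so.

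**Conclusion.** The point holds, as a cheap improvement. Whenever new cancer treatment starts before day 30, the SAE and ECI window is t days against 30 for AEs. A non-fatal serious event between day t and day 30 is recorded as an AE but lies outside SAE collection, and it is unclear whether the reporting duties in Section 16.7 apply. The reversal follows from the text alone; it assumes only that the differently worded end-of-treatment clocks mean the same day.

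Two stronger readings are not supported:
- *Late immune-related events are lost through this gap.* Section 8.1.1 does say that such events can appear months after the last dose. But the reversal exists only before day 30, and a 30-day minimum would recover no later event in a patient who has switched. The cut-off after day 30 is a separate, consistently stated choice.
- *A particular number of patients is affected.* The documents give no switching rate. Any count would rest on an assumed rate and on dosing continuing up to the last scan, and it would count fast switchers, when only those with a non-fatal SAE or ECI in the gap matter. If dosing is held during the 4 to 8 week confirmation, the situation would be uncommon.

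**What to change.** In Sections 7.8, 16.6.2 and 16.8, state that SAEs and ECIs are collected and reported to day 30 after the last dose regardless of new therapy, and from then to day 90 or the start of new cancer treatment, whichever is first. Check that Section 16.6.1 reads consistently with this. If those sections are being edited anyway, add that the death sentence in 16.6.2 supplements the SAE rule and does not limit it.

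The change is to wording on data collection and reporting, and leaves treatment and patient management as they are. The cost is a few more SAE reports, some of them attributable to the next therapy; recording the start date of that therapy on the report would help readers judge attribution.
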